## **I. BACKGROUND AND SIGNIFICANCE**

The shoulder joint is the most common joint requiring reduction by emergency physicians, accounting for almost 50% of all major joint dislocations. This presentation amounts to roughly 200,000 emergency department visits each year. The estimated incidence of shoulder dislocations in the United States is 23.9 per 100,000 person/year with male gender and young age being the two largest risk factors. The current standard of care for this presentation is to identify the dislocation on both physical exam and X-ray and then confirm the success of reduction by physical exam and X-ray following reduction. X-ray imaging does expose the patient to radiation, although minimally when as compared to other radiation-based imaging. However it is now being recommended by one study that pre and post-reduction X-rays can be omitted to help decrease the length of stay, radiation exposure and overall cost. The recommendation is that X-ray can be replaced with the application of ultrasonography. The aim of this study is to further assess the efficacy of point of care ultrasonography to diagnose and gauge the reduction success of shoulder dislocations in an emergency department setting.

With increasing availability and utilization of ultrasound, multiple studies suggest that this imaging modality can play an integral role in the diagnosis of and reduction confirmation for shoulder dislocations. Studies assessing accuracy of diagnosis deemed ultrasound to be 100% specific and 100% sensitive. A recent meta-analysis concluded that ultrasound is highly sensitive and specific for shoulder reductions, dislocations, and associated fractures. Another study identified that diagnostic radiographs increased patient length of stay by 30 minutes. The ease, efficacy, and timeliness of ultrasound has the potential to decrease the length of stay for emergency department patients. A WJEM systematic review recommended that “while the data is supportive of the use of ultrasound for the diagnosis of shoulder dislocation, further studies are needed prior to routine implementation. Future studies should compare the different techniques to determine which is most

accurate, record performance time for the ultrasound, include more data on posterior dislocations, include more data on fracture identification, and validate one of the above techniques with increased sample sizes".

Overall, the utilization of point of care ultrasonography has been well studied and has recurrently shown to be useful and efficacious. The goal of this study is to expand on this literature as it pertains to utilization in the emergency department setting. The study will evaluate the impact of POCUS on length of stay, x-ray reduction, and satisfaction of patients presenting with suspected shoulder dislocation.

## II. STUDY OBJECTIVE(S); INCLUDING SPECIFIC AIMS AND/OR HYPOTHESES

The primary objective of this study is to determine if there is any difference in the length of stay between patients with shoulder dislocation who are treated with traditional x-ray imaging for diagnosis and reduction confirmation and those that are treated with POCUS for diagnosis and reduction confirmation.

*Hypothesis:* The use of POCUS for shoulder dislocation and reduction confirmation will reduce the length of stay for ED patients.

The secondary objectives of this study include evaluating patient satisfaction, providing a cost analysis, time to diagnosis, confirmation of reduction, and volume of x-ray reduction.

## III. METHODS

This study is a prospective, randomized, non-blinded evaluation of the use of ultrasound to diagnosis shoulder dislocation in emergency departments. The study population will consist of patients aged 18-65 that present to the VCU Emergency Department between August 1, 2020 and December 31, 2022 with suspicion of an uncomplicated shoulder dislocation.

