### Procedural Overview/Design:

1. Assess patient for enrollment. Apply inclusion and exclusion criteria (below).
2. Discuss Informed consent with patient. If patient consents, proceed to step 3.
3. Randomize patient with premade numbered envelopes stating standard of care or ultrasound protocol (description below).

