#### A. Diagnosis of dislocation

1. **Standard of Care (control):** Order shoulder x-rays as felt necessary for standard of care of diagnosis of shoulder dislocation and reduction (portable XR versus done in radiology)

**2. Ultrasound (experiment):** No x-rays ordered. Initial evaluation with ultrasound; may also evaluate nearby areas for concern of fracture. Order x-rays after ultrasound as seen fit for other injuries of diagnostic uncertainty.

B. Shoulder reduction: Per standard of care

C. Confirmation of Reduction

- Standard of Care (control):** Order shoulder x-rays as felt necessary for standard of care of reduction confirmation.
- Ultrasound (experiment):** Use ultrasound for reduction confirmation. No x-rays ordered unless ultrasound did not adequately confirm

D. Post-reduction care (sling, follow-up, etc.): Per standard of care

	Control Group	Experimental Group
Diagnosis of Dislocation	Standard of Care (x-ray)	Ultrasound
Shoulder Reduction	Per Standard of Care	Per Standard of Care
Confirmation of Reduction	Standard of Care (x-ray)	Ultrasound

B. Study Population:

*Inclusion Criteria:*

1. Patients who are 18 years of age or older; *and*
2. Present to the VCU Emergency Department between August 1, 2020 and December 31, 2022; *and*
3. Have clinical signs of uncomplicated shoulder dislocation; *and*
4. Agree to participation in the study; *and*
5. Provides a written consent to be included in the study.

*Exclusion criteria:*

1. Patients who have a level 1 or 2 trauma activation, and/or;
2. Patients who are pregnant, incarcerated, or unable to consent, and/or;
3. Patients who have a past medical history of shoulder replacement in dislocated shoulder; and/or
4. Provider Discretion

E. Assessment of Resources

*1. Has sufficient access to the study population:*

Emergency Medicine attending and resident physicians will perform the study. They will already be in the Emergency Department and therefore will be notified of a patient meeting inclusion criteria and immediately be able to complete study following consenting process.

*2. Has sufficient time to conduct and complete the study:*

This will be a long-term project in the emergency department. Not all ED physicians will be participating in this study. The resident physicians and a select group of attending physicians will receive a curriculum and conduct the study.

*3. Has adequate qualified staff members to conduct the study:*

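### Eligibility contradicts itself: age is 18-65 in one place and 18 or older in another, and a single named ED sits beside a multicenter description

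*Combined protocol and SAP*

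**What the plan says.** **Age.** Section III, Methods, opens with the population: "The study population will consist of patients aged 18-65 that present to the VCU Emergency Department". Step 1 of the Procedural Overview is "Assess patient for enrollment. Apply inclusion and exclusion criteria (below". That list, under Study Population, begins with "Patients who are 18 years of age or older". The four exclusions cover trauma activation, a group comprising pregnancy, incarceration and inability to consent, earlier replacement of the dislocated shoulder, and "Provider Discretion". None mentions age.

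**Site.** Inclusion criterion 2 is "Present to the VCU Emergency Department between August 1, 2020 and December 31, 2022", which matches the Methods sentence. Assessment of Resources also speaks of one department: "This will be a long-term project in the emergency department". Section V.A (Sample Size Considerations), however, calls the study multicenter. Section VII (Study Limitations) foresees difficulty in obtaining ethics approval from every institution. Section IX (Plans for Dissemination) refers to institutions in the VCU network. No section lists the sites.

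**Data and analysis.** Section IV lists demographics (including age), history, procedure data, ED timeline and a satisfaction survey. It has no entry for the enrolling ED. Section V.B names a paired t-test for the primary outcome, ED length of stay, and for the secondary outcomes.

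**The concern.** Eligibility is the first thing staff decide, and two of its elements have no single answer in the current text. A 70-year-old who meets the other criteria passes the list but is not in the population that Methods describes. A patient at a second network ED fails criterion 2 if it is read literally, yet belongs to the study that Sections V.A, VII and IX describe.

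At stake is the definition of the study population, and so whom the length-of-stay result applies to. Study Limitations itself ties external validity to the inclusion and exclusion criteria. If several EDs do enrol, length of stay may differ between them, and the plan as written does not provide for recording which ED a patient came from.

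**Working it through.** The documents give no figure to reproduce on this point: no sample size, SD, number of EDs or age distribution. The check is mainly a comparison of texts.

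**1. Texts side by side**

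| Element | One statement | Conflicting statement | Resolved elsewhere? |
|---|---|---|---|
| Upper age | 65 (III, Methods) | None (inclusion criterion 1) | No; no exclusion on age |
| Site | VCU ED (III, Methods; criterion 2) | Multicenter, several institutions (V.A, VII, IX) | No; no list of sites |

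The eligibility text agrees with itself on site. The conflict is with the later sections.

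**2. Effect on the arm comparison.** The Procedural Overview applies the criteria at step 1 and opens the envelope at step 3. Whichever rule is used, it acts before assignment and so equally on both arms. It changes who is compared, not the fairness of the comparison.

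**3. How often the age conflict could arise.** Background reports "male gender and young age being the two largest risk factors", so the share over 65 may be small, but no share is given. I assume a share p of 2%, 5% or 10% and N of 40, 60 or 100. The expected number is N × p, and the chance of at least one is 1 − (1 − p)^N.

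| p | Expected number, N = 40 / 60 / 100 | Chance of at least one |
|---|---|---|
| 2% | 0.8 / 1.2 / 2 | 0.554 / 0.702 / 0.867 |
| 5% | 2 / 3 / 5 | 0.871 / 0.954 / 0.994 |
| 10% | 4 / 6 / 10 | 0.985 / 0.998 / >0.999 |

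The numbers are small, but across these assumptions the case is more likely than not to occur.

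**4. Recording the ED.** Going through every list in Section IV, survey included, finds no site, ED or institution field. Section VI has the data de-identified for analysis once collected, so a field that is wanted has to be planned before that step.

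**5. The test.** A paired t-test works on differences within pairs. Here each patient is randomised individually by envelope and contributes one length of stay under one arm. The documents describe no matching, so there are no pairs to difference. This is true with one ED or with several. The same section already names the independent-groups tests for continuous variables: Student's t-test, or Mann-Whitney when the data are not normal.

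**The case against.** **The criteria list governs, and the Methods sentence is only a summary.** This is the best answer on age. Staff are indeed sent to the list, which gives them a working rule. But no section gives the list precedence, and if it has precedence then the Methods sentence is wrong and still needs correcting. Provider discretion does not supply an age limit; it leaves the matter to each physician.

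**VCU Emergency Department may be meant loosely, for all network EDs.** Methods does call the study an "evaluation of the use of ultrasound to diagnosis shoulder dislocation in emergency departments", in the plural. The reading is possible, but nothing states it. The Confidentiality section keeps all data on-site at VCU, which concerns storage and does not settle who enrols.

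**The harm is limited.** This stands. Age is a collected field and demographics will be summarised, so the enrolled range can be reported and patients over 65 identified. If only one ED enrols, the missing field costs nothing.

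A reader might infer more than the documents support:

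- *That the treatment comparison is biased.* It is not, because eligibility precedes randomisation.
- *That the ED could never be described or adjusted for.* Section IV draws the patient list and part of the data from the electronic record, so ED may be recoverable. The supportable statement is that its recovery is not planned.
- *That adjusting for ED would clearly sharpen the result.* The inputs are missing. Assume three equally likely EDs (K = 3), a within-ED SD of 90 minutes, equal steps between the ED means, and simple randomisation. The variance ratio, adjusted to unadjusted, is then about 8100/(8100 + ((K² − 1)/12) × step²) × (N − 3)/(N − K − 2). With 60-minute steps and N = 100 it is 8100/10500 × 97/95 = 0.788, a 21% fall. With no ED differences and N = 40 it is 37/35 = 1.057, a 6% rise. Even the sign depends on the assumptions.
- *That the paired test would be acceptable at a single site.* It would not.

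**Conclusion.** The point holds as an internal inconsistency in eligibility, on age and on site, in current text that nothing else in the documents resolves. It should be corrected but is not fatal: no bias between arms follows from it. Its consequence is that the eligibility of a patient over 65, or at another network ED, cannot be determined, and the target population is correspondingly unclear.

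On the assumed shares and sample sizes, between 0.8 and 10 patients over 65 would be expected, with a 55% or higher chance of at least one. These figures illustrate scale and are not estimates for this trial. The missing ED field matters only if more than one ED enrols, and the gain or loss from adjusting for ED cannot be quantified from the documents. The mismatch between the paired t-test and independent arms depends on none of these assumptions.

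**What to change.** In one amendment:

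1. Reconcile the age range so that the Methods sentence and inclusion criterion 1 state the same one. The sponsor chooses which.
2. Reconcile the site wording. Either name every participating ED in Methods and in criterion 2, or remove the multicenter and multi-institution wording from Sections V.A, VII and IX.
3. If more than one ED enrols, add enrolling ED to the Section IV data fields, to be captured before de-identification.
4. Whatever the number of EDs, replace the paired t-tests in Section V.B with independent-groups comparisons. If several EDs enrol, an ED term in the length-of-stay analysis is optional.

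The cost is a short text change and, under item 3, one added field that the electronic record may be able to supply. Item 4 needs no new method, since the section already names suitable tests. The optional ED term may lose a little precision if the EDs do not differ.

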### Procedural Overview/Design:

1. Assess patient for enrollment. Apply inclusion and exclusion criteria (below).
2. Discuss Informed consent with patient. If patient consents, proceed to step 3.
3. Randomize patient with premade numbered envelopes stating standard of care or ultrasound protocol (description below).

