### VI. DATA AND SAFETY MONITORING PLAN (if applicable)

This data will be stored behind the VCU firewall and on Redcap and if any transfer of data is necessary this will be done on RedCap. Once the data is collected the data will be de-identified for analysis.

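### Allocation by numbered envelopes in an open-label trial has no described safeguard against the next assignment being read ahead, guessed or skipped; concealed central randomisation would largely close the gap

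*Combined protocol and SAP*

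**What the plan says.** Section III (Methods) calls the study a "prospective, randomized, non-blinded evaluation". Under Procedural Overview/Design, eligibility is assessed first and consent second ("If patient consents, proceed to step 3"). Step 3 is the only text on allocation: "Randomize patient with premade numbered envelopes stating standard of care or ultrasound protocol".

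The fourth exclusion criterion under Study Population reads, in full, "Provider Discretion". Assessment of Resources, item 1, says that "Emergency Medicine attending and resident physicians will perform the study"; item 3 adds that residents or medical students who deal with patients will be trained in consenting.

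Section V.B (Statistical Methodology) compares mean emergency department length of stay with a t-test and names no covariates. Section V.A describes the study as multicentre, although the eligibility criteria name one department. Section VI says of the data: "This data will be stored behind the VCU firewall and on Redcap". It gives REDCap no role in randomisation.

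**The concern.** Taking consent before opening the envelope protects the comparison only if nobody involved in enrolment knows or can guess the next assignment when the patient is approached. If they can, an exclusion without criteria becomes a way to choose patients by arm. A likely slow case can be passed over when one card is next and enrolled when the other is.

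Three features make this matter here. Without blinding, staff see past assignments. The people performing the study work in the department and have a stated hypothesis that ultrasound shortens the stay. The primary outcome also depends heavily on case complexity, and an unadjusted t-test does nothing about arms that differ in complexity at entry. Section VII (Study Limitations) mentions selection bias only as a threat to external validity, not as a possible difference between arms.

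**Working it through.** The plan states no sample size, allocation ratio, block size, standard deviation or target difference, so it has no figure of its own to reproduce. The check has three parts.

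**1. Which safeguards are described**

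| Element | In the protocol |
|---|---|
| Consent before the envelope | Stated |
| Envelopes numbered | Stated; no instruction to open them in order |
| How the sequence is generated; ratio, blocks, site strata | Not stated |
| Envelopes sealed and opaque | Not stated |
| Who prepares, keeps and opens them | Not stated |
| Record of patient, date and time at opening | Not stated |
| Log of patients excluded at discretion | Not stated |

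**2. Size of the bias if assignments are known (all inputs assumed)**

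- p = 0.25, the share of eligible patients who are complex.
- e = 60 or 90 minutes, their extra stay.
- k = the chance, for each patient approached, that a next card of ultrasound is known in advance. Every complex patient in that position is withheld and does not return.
- The control arm is unaffected and keeps a complex share of p.

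The complex share in the ultrasound arm is p(1 − k)/(1 − kp), so

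bias = e × [p(1 − k)/(1 − kp) − p].

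| k | Complex share, ultrasound arm | Difference from 0.25 | e = 60 | e = 90 |
|---|---|---|---|---|
| 0.2 | 0.20/0.95 = 0.2105 | −0.0395 | −2.4 min | −3.6 min |
| 0.5 | 0.125/0.875 = 0.1429 | −0.1071 | −6.4 min | −9.6 min |
| 1.0 | 0 | −0.25 | −15 min | −22.5 min |

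If knowledge instead stays with a given card until it is used, the complex share is p(1 − k) and the bias is −kpe: −3.0 and −4.5 minutes at k = 0.2, −7.5 and −11.25 at k = 0.5, and the same values at k = 1. If complex patients are withheld from the control arm instead, every sign reverses.

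The same algebra covers a card that is always visible but with only some slow patients kept out. Let f be the slow share (0.3 to 0.5), D the extra stay (60 to 120 minutes) and q the chance of being kept out (0.1 to 0.5). The size ranges from 60 × [0.3 − 0.27/0.97] = 1.3 minutes to 120 × [0.5 − 0.25/0.75] = 20 minutes.

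The only time figure in the documents is the 30 minutes attributed to diagnostic radiographs in Section I. It is background, not a design effect.

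**3. What remains after central randomisation**

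If past assignments and the block size are known, the expected share of next assignments guessed correctly is 75% for 1:1 blocks of 2, 70.8% for blocks of 4 and 68.3% for blocks of 6, against 50% under simple randomisation.

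A simulation with no true effect used 100 patients, f = 0.5, D = 120 minutes, q = 0.5, a residual SD of 60 minutes, a two-sided unpaired t-test at 0.05 and 3,000 runs:

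| Allocation | Mean false difference | Type I error |
|---|---|---|
| Next card visible | −20.1 min | 22.3% |
| Concealed, known fixed blocks of 2 | −10.3 min | 8.9% |
| Concealed, known fixed blocks of 4 | −8.2 min | 7.5% |
| Concealed, known fixed blocks of 6 | −7.0 min | 6.8% |
| Concealed, simple randomisation | −0.5 min | 4.8% |

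With q = 0.25 the visible-card case falls to −8.4 minutes and 7.3%. Concealment removes advance sight of the card. Unpredictability of the sequence has to be secured separately.

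**The case against.** The strongest reply is that silence is not a defect. Numbering is itself a sequence control, and consent comes first. If the envelopes are sealed, opaque and opened in order, the next card cannot be read, and only guessing or tampering remains. This is partly right, and the fix below keeps such envelopes as a fallback. But the protocol states none of these conditions, and envelopes leave no automatic record of when one was opened or for whom. A method that does is within reach at small cost.

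Several stronger readings are tempting, and the documents do not support them:

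- **That the treating physicians hold and open the envelopes, or that assignments are visible.** The first is a natural inference from who performs the study, but custody and opening are not described. Neither is any defect in the envelopes.
- **That the bias must favour ultrasound.** No motive is documented. Operators with minimal experience, a category recorded under Data Collection, might avoid scanning difficult cases. Keen operators might seek them out.
- **That the larger figures are expected values.** At k = 1 the ultrasound arm contains no complex patient at all, which is a worst case. Entry is limited to uncomplicated dislocations, and the higher trauma activations are excluded, so a large slow subgroup is not obvious.
- **That the selection could never be detected.** Age, weight, insurance status and prior dislocations are collected, so imbalance might hint at it and allow partial adjustment. Unmeasured selection would remain.
- **That REDCap would remove the bias.** It is named only for storing and transferring data, its randomisation function may not be enabled, and a guessable list would leave some bias.

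**Conclusion.** The point holds as an unguarded risk to the primary comparison, and the change should be made. In an open-label trial with an exclusion that has no criteria, the described procedure does not prevent the next assignment from being read ahead, guessed or skipped, and the planned analysis would not correct for it. A reader might infer that allocation is being subverted; the documents give no evidence of that.

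The size cannot be derived from the documents. Under the assumptions in part 2 it runs from about 2 to 4 minutes when one approach in five is compromised, through 6 to 10 at one in two, to a worst case of 15 to 23. Even the middle range is not negligible beside the 30-minute background figure: 6.4/30 = 21% and 9.6/30 = 32%. The direction depends on clinicians' motives. Central randomisation would largely, not fully, remove the risk.

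**What to change.** Replace the envelopes with central electronic randomisation, for example REDCap's randomisation function once the institution confirms that it is enabled:

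- The list is prepared and loaded by someone who does not enrol patients.
- Permuted blocks vary in size, the sizes are not disclosed to enrolling staff, and allocation is stratified by hospital if more than one enrols.
- The assignment is released only after eligibility and consent are entered, and is irreversible and time-stamped.
- Every exclusion made at the provider's discretion is logged with its reason before any assignment is released.

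If electronic release is unavailable or down, use sequentially numbered, sealed, opaque envelopes prepared by someone who does not enrol patients, with patient, date and time recorded on opening.

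The cost is a one-time set-up, a device at enrolment and about a minute per patient. REDCap is already named for the trial's data, and Assessment of Resources already lists computers for data work, but use at the bedside would need to be confirmed.
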